1.5 MODIFICATIONS TO THE STATISTICAL SECTION OF THE PROTOCOL

Additional secondary endpoint CGM parameters are added to assess glucose variability and some clarifications of the definition of CGM parameters are included in the statistical analysis plan.

1.6 STATISTICAL MODIFICATIONS MADE IN THE STATISTICAL ANALYSIS PLAN

Three statistical modifications were made in the statistical analysis plan.

- 1) Per protocol, during Week 15, patients will wear a blinded CGM device for 7 consecutive days to generate a minimum 4 days of useable CGM data. If a patient fails the first attempt for any reason, he/she will be retrained for CGM conduct and complete another course of blinded CGM in Week 16. If the patients fails the first week of CGM, only the second week CGM data will be used for data analysis and determine whether there are sufficient data to derive CGM variables. A statistical modification was made that if the second week CGM data are not sufficient per steps 1-6 above either and two weeks pooled together can generate a minimum 4 days of usable CGM data, then CGM data from both weeks will be pooled together to derive CGM variables.

- 2) An additional secondary endpoint, the mean change of each participant's glucose level during the last four hours of CGM data collection prior to next day's basal insulin injection, was added.
- 3) If there are more than hypoglycemia events within 30 minutes interval, the one with the lowest glucose level will be used.

2 STATISTICAL AND ANALYTICAL PROCEDURES

2.1 ANALYSIS ENDPOINTS

2.1.1 Demographic and baseline characteristics

Baseline CGM measurements will start at Visit 2 and stop at randomization visit (Visit 3).

The baseline value for other efficacy and safety parameters is defined as the last available value before randomization visit (Visit 3).

All baseline safety and efficacy parameters (apart from those listed below) are presented along with the on-treatment summary statistics in the safety and efficacy sections ([Section 2.4.5](#) and [Section 2.4.4](#)).

Demographic characteristics

- Age (years),
- Age group (<65 and ≥65 years of age)
- Gender (Male, Female),
- Race (Caucasian/white, Black, Asian/Oriental, other),
- Ethnicity (Hispanic, non-Hispanic)
- Randomization strata of HbA1c obtained at the screening visit (<8.0% vs ≥8.0%), Frequency of Lantus injection at screening (BID vs QD), Lantus injection at screening (AM vs PM), current CGM use (yes/no) and mealtime insulin titration algorithm (carbohydrate counting versus simple titration).

Medical or surgical history

All medical/surgical history information, pre-listed or not in the CRF, will be coded using the version of Medical Dictionary for Regulatory Activities (MedDRA) currently in effect at Sanofi at the time of database lock.

Disease characteristics at baseline

- Age at diagnosis of diabetes (years),
- Diabetes duration (years),

Specific disease history includes:

- Mealtime/bolus insulin at randomization (insulin glulisine, insulin lispro, and insulin aspart).
- Diabetic complications (including microvascular and neuropathic complications)
 - Diabetic retinopathy (yes/no/unknown),
 - Diabetic sensory or motor neuropathy (yes/no/unknown),
 - Diabetic nephropathy (yes/no/unknown).

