1 FLOW CHARTS

1.1 GRAPHICAL STUDY DESIGN

1.2 STUDY FLOW CHART

	Scree traini	ening an ng	d					Treatment Period (15-16 weeks)								Follow up				
Visit Windows: Visit 4 - 19: ± 3 days	1	2*	3	4 ^a ≅	5 ^a	6 ^a	7	8 a	9 ^a	10 ^a	11	12 ⁸	13 ^a	14 ^a	15	16 ^a	17 ^a	18 ^b	19	20 ^a
Week	-4	-3 -1	(R)	1	2	3	4	5	6	7	8	9	10	11	12	13	14	15	16	2+2 days
Informed consent	Χ																			
Inclusion/Exclusion criteria	Χ	Χ	Χ																	
Medical and surgical history; diabetes history	Χ																			
Physical examination, including neuropathy screening	Х																			
Vital signs ^C and Body weight	Χ		Χ				Х				Χ				X				X	
Height	Χ																			
Dispensation/collection of study diary	Χ	Х	Χ				Χ				Χ				Χ			Χ	Х	
Dispensation of study medication			Χ				X				Χ				Χ					
IMP compliance Check; collecting and counting used and unused pens							X				X				X			X	X	
IVRS call	Χ		Χ				Χ				Χ				Χ				Χ	
Randomization			Χ																	
Documentation and review of basal and bolus insulin dose	Х	Х	Х	Х	Х	Х	Х	Х	Х	Х	Х	Х	Х	Х	Х	Х	Х	Х	Х	
Change from BID to QD basal insulin injection (if applicable)		Х																		
CGM, SMPG:										•										
Training and re-training: Glucometer, SMPG profiles, study diary	Х	Х	X				Х				X				X			Х		
Dispensation glucometer,	Χ																			
Dispensation CGM device; Blinded CGM ^d		Χ																Χ		
Upload CGM to PC			Χ			 			 	 			 						Х	
Collect CGM device			Χ							 			 						X	
SMPG ^e	Х	Х	Х	Х	Х	Х	Х	Х	Х	Х	Х	Х	Х	Х	Χ	Х	Х	Х	Х	
Upload SMPG to PC		Х	Χ				Χ				Χ				Χ			Χ	Х	
Concomitant medication	Χ	Х	Χ	Х	Х	Χ	Χ	Х	Х	Χ	Χ	Х	Χ	Χ	Χ	Х	Χ	Χ	Х	Х
Central Laboratory						•			•	•				•			•			
HbA1c, Fasting plasma glucose (FPG)	Χ										Χ								Χ	

Amended Clinical Trial Protocol No. 01 LPS14587 - insulin glargine

02-Aug-2016 Version number: 1

	Scree trainii	ning an ng	d		Treatment Period (15-16 weeks)									Follow up						
Visit Windows: Visit 4 - 19: ± 3 days	1	2*	3	4 ^a	5 ^a	6 ^a	7	8 a	9 ^a	10 ^a	11	12 ^a	13 ^a	14 ⁸	15	16 ^a	17 ^a	18 ^b	19	20 ^a
Week	-4	-3 -1	(R)	1	2	3	4	5	6	7	8	9	10	11	12	13	14	15	16	2+2 days
C-peptide ^f	X																			
Safety Laboratory																				
Hematology ^g , Clinical Chemistry ^h	Х																			
Urine analysis ⁱ	Χ																			
Pregnancy test (WOCBP only) ^j	Χ		Х				Χ				Х				Х				Х	
AE / SAE	To be	assesse	ed and re	eported	(if any) t	hrougho	ut the s	tudy (re	port SAI	E to the	sponsor	within 2	4 hours)						

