10.2 ASSESSMENT METHODS

10.2.1 Vital signs

Determination of the reference arm for blood pressure measurements: At visit 1 after the patient has rested comfortably for at least 10 minutes, blood pressure has to be measured on both of the patient's arms while the patient is **in sitting position** and then again after two minutes on both arms. The arm with the higher diastolic blood pressure will be determined at this visit, identifying the reference arm for future measurement throughout the study. The highest value will be recorded in the e-CRF (all blood pressure values are to be recorded in the source data).

Blood pressure at all subsequent visits should be measured when the patient is quiet and seated and with their determined reference arm outstretched in line with mid-sternum and supported. Measurement at all subsequent visit should be taken under standardized conditions, approximately at the same time of the day, on the reference arm, with the same device (after the patient has rested comfortably for at least five minutes) and the values are to be recorded in the e-CRF. Both systolic blood pressure (SBP) and diastolic blood pressure (DBP) should be recorded. Devices for blood measurement should be regularly recalibrated according to manufacturers' instructions.

Heart rate will be measured at the time of the blood pressure measurement.

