11.4.3 Analyses of safety data

All safety and tolerance results will be presented by treatment group and on the safety population using the following common rule that the baseline value will be defined generally as the last available value prior to the first injection of IMP.

For all safety data, the observation period will be divided into three segments:

- The pre-treatment phase is defined as the time between when the patients give informed consent and time of the first IMP administration (excluded).
- The on-treatment phase is defined as the time from the first IMP administration (included) until 1 day after the last dose of IMP (until midnight of day after last IMP dosing day).

The post-treatment phase is defined as the time after the on-treatment phase until the end of treatment.

Adverse events

The primary focus of AE reporting is on TEAEs. Pre- and post-treatment AEs are described separately. If an AE date/time of onset (occurrence, worsening, or becoming serious) is incomplete, an imputation algorithm is used to classify the AE as pre-treatment, TEAE, or post-treatment. The algorithm for imputing date / time of onset is conservative and classifies an AE as

a treatment emergent unless there is definitive information to determine it is pre- or post-treatment.

The following TEAEs will be summarized: Overall TEAEs, serious TEAEs, TEAEs leading to death, TEAEs leading to permanent treatment discontinuation. TEAEs will also be summarized by relationship to study treatment, and by severity. All treatment emergent SAEs will also be presented separately.

Adverse event incidence tables will present the number and percentage of patients experiencing an AE by SOC, high level group term (HLGT), high level term HLT and preferred term (PT) sorted by internationally agreed order for SOC and in alphabetical order of HLGT, HLT and PT within a SOC for each treatment group. Multiple occurrences of the same event in the same patient is counted only once in the tables within a treatment phase. The denominator for computation of percentages is the safety population within each treatment group.

Injection site reactions and hypersensitivity reactions

The number and percentage of patients experiencing injection site reactions and hypersensitivity reactions will be summarized separately.

Death

The following deaths summaries will be generated:

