2.1.3 Efficacy endpoints

The baseline value for efficacy parameters is defined as the last available value before the first injection of IMP.

Baseline CGM measurements will start at Visit 2 and stop at randomization visit (Visit 3).

Observation period for efficacy endpoints

- The on-treatment period for efficacy variables is defined as the time from the first dose of IMP up to:
 - Seven (7) days after the last dose of IMP for HbA1c,
 - One (1) day after the last dose of IMP for hypoglycemia,
 - One (1) day after the last dose of IMP for FPG, SMPG and CGM,
 - Zero (0) day after the last dose of IMP for insulin glargine dose.
- The randomized period for efficacy variables is defined from the first dose of IMP up to Week 16 (visit 19).

All efficacy parameters will be performed on on-treatment period and randomized period.

All CGM derived variables will be subject to the following criteria.

1. CGM data are blinded to both the patients and investigators.
2. During the CGM performing week, the IMP insulin (Toujeo or Lantus) dose is fixed without a change, while the mealtime insulin dose can still be adjusted appropriately.

3. A complete 24-hour CGM profile includes 288 data points given that CGM reading is recorded every 5 minutes.
4. The start and end time of a 24-hour CGM profile is defined as midnight. i.e. each CGM profile begins at midnight (hour 0) and ends at midnight (hour 24 = hour 0). Partial CGM data points prior to the first midnight and after the last midnight from the visit will not be used in the CGM parameter calculation as the partial CGM profile may introduce additional variabilities to the data.
5. Useable CGM data for a day/a 24-hour CGM profile are defined as at least 85% time of records (245 data points) without a gap (missing data) lasting for ≥ 2 hours per 24 hours. At least 4 days of qualified 24-hour CGM records for each patient will be used for efficacy analyses. If the partial CGM data described in previously have at least 85% of a full CGM profile or 245 data points, the partial CGM profile will be used to calculate CGM parameters.
6. In cases that there are more than 288 data points or more than one data point per 5 minutes, usually due to recalibration or switching CGM devices, it will be reviewed and treated case by case. Usually averaging the data points every 5 minutes will be performed so that there is only one data point per 5 minutes.

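### SAP 2.1.1 takes the safety baseline before Visit 3, against Protocol 11.4.3; applied literally, this makes Visit 1 the blood-pressure baseline and tends to produce an artificial fall

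*SAP*

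**What the plan says.** **Baseline rules.** For safety parameters, and for efficacy parameters other than CGM, SAP 2.1.1 states that the baseline value "is defined as the last available value before randomization visit (Visit 3". Protocol 11.4.3 states for safety data that "the baseline value will be defined generally as the last available value prior to the first injection of IMP". SAP 2.1.3 states for efficacy parameters that baseline "is defined as the last available value before the first injection of IMP". SAP 1.5 and 1.6, which record changes from the protocol, do not mention the safety baseline.

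**Schedule.** In the flow chart (Protocol 1.2), the row "Vital signs ^C and Body weight" is marked at Visits 1, 3, 7, 11, 15 and 19. Visit 2 is blank. Under Protocol 10.1.2 the first dose is injected at Visit 3, after randomization.

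**Blood pressure procedure (Protocol 10.2.1).** At Visit 1, after at least 10 minutes of rest, pressure is taken on both arms "and then again after two minutes on both arms". The arm with the higher diastolic pressure becomes the reference arm. Then: "The highest value will be recorded in the e-CRF". All the readings stay in the source data. At later visits pressure is taken on the reference arm after at least 5 minutes of rest; neither repeat readings nor a highest-value rule is stated.

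**Analysis.** Protocol 11.4.3 plans descriptive summaries, by treatment, of absolute values and changes from baseline for all vital signs including weight. SAP 2.1.4 lists vital signs among the safety parameters, but SAP 2.4.5 contains no vital-sign analysis.

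**The concern.** The two documents give different baseline rules for the same safety data, and the schedule makes the difference matter. Under the protocol rule a pre-dose Visit 3 value is the baseline. Under the SAP rule, read literally, Visit 3 is excluded and the scheduled baseline falls back to Visit 1.

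For blood pressure, the two visits are recorded under different rules. A value chosen because it was the highest of several lies above the patient's usual level on average, so later unselected readings will appear to have fallen even with no true change. The within-arm change-from-baseline table would carry that artifact in both groups.

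For pulse and weight there is no selection rule. Their baseline simply moves earlier, into screening.

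**Working it through.** The documents give no figure for blood pressure or its variability, so there is nothing to reproduce. The check traces the rule and then sizes the artifact under stated assumptions.

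**Step 1: which visit becomes baseline?**

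| Rule | Vital-sign visits that qualify | Scheduled baseline |
|---|---|---|
| Protocol 11.4.3 (before first injection) | Visit 1, and Visit 3 if pre-dose | Visit 3 |
| SAP 2.1.1, literal (before Visit 3) | Visit 1 only | Visit 1 |

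HbA1c and FPG are scheduled at Visits 1, 11 and 19, so both rules give Visit 1 for them. CGM has its own baseline window. The conflict between SAP 2.1.1 and SAP 2.1.3 therefore does not move those scheduled baselines.

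**Step 2: how many readings at Visit 1?** 2 arms × 2 times = 4.

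**Step 3: expected systolic excess with no true change.** Assumptions, none from the documents:

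- systolic within-visit SD *s* of 3 to 8 mmHg, with independent normal errors between readings;
- diastolic SD 0.6*s*, and systolic–diastolic correlation 0.6;
- a persistent arm difference with SD 0 or 3 mmHg per arm.

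The sentence on the highest value can be read in three ways. With no persistent arm difference the systolic excess is:

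- **A. Highest of all four, systolic and diastolic separately.** The expected maximum of 4 normal readings is 1.03*s*: 1.03 × 3 = 3.1, 1.03 × 5 = 5.1 (rounded down from 5.15), 1.03 × 8 = 8.2 mmHg.
- **B. Higher of the two reference-arm readings.** The expected maximum of 2 is 0.56*s*. Choosing the arm on its mean diastolic pressure adds 0.6 × 0.56*s*/√2 = 0.24*s*. The sum is 0.80*s*: 2.4, 4.0 and 6.4 mmHg at *s* = 3, 5 and 8.
- **C. The reading with the highest diastolic pressure, with its paired systolic.** 0.6 × 1.03*s* = 0.62*s*: about 1.9, 3.1 and 4.9 mmHg.

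A simulation of 400,000 patients with no treatment effect and no time trend gave these expected falls from Visit 1 to later reference-arm readings (mmHg, at *s* = 3 / 5 / 8):

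| Reading | Systolic, arm SD 0 | Systolic, arm SD 3 | Diastolic, arm SD 0 | Diastolic, arm SD 3 |
|---|---|---|---|---|
| A | 3.09 / 5.14 / 8.24 | 3.07 / 5.05 / 8.12 | 1.86 / 3.08 / 4.95 | 1.51 / 2.76 / 4.68 |
| B | 2.41 / 4.02 / 6.44 | 2.11 / 3.74 / 6.20 | 1.74 / 2.88 / 4.63 | 1.43 / 2.61 / 4.40 |
| C | 1.86 / 3.08 / 4.95 | 1.51 / 2.76 / 4.68 | 1.86 / 3.08 / 4.95 | 1.51 / 2.76 / 4.68 |

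The fall is positive in every cell. Across readings the systolic range is about 1.5 to 8.2 mmHg.

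**Step 4: between arms.** Visit 1 precedes randomization and the procedure is the same for everyone, so the expected artifact is equal in both groups and its expected difference is 0.

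**Step 5: with the protocol rule.** A pre-dose Visit 3 reading on the reference arm is taken in the same way as later readings, so the expected artifact is 0.

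**Step 6: weight and pulse.** The flow chart places Visit 1 at Week −4, so change to Week 16 would span up to 4 + 16 = 20 weeks rather than 16. Protocol 10.1.1.2 and 10.1.2 put Visit 2 about one week after Visit 1 and Visit 3 seven days later, so without a repeated CGM course the span is nearer 2 + 16 = 18 weeks. No direction of bias follows from this.

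**The case against.** The strongest reply is that the only planned vital-sign change-from-baseline analysis sits in Protocol 11.4.3, which carries its own baseline rule. Followed on its own terms, that section allows Visit 3 and there is no artifact. The problem arises only if the SAP 2.1.1 definition is put into the protocol's analysis. This stands, and it is why the point is conditional. It does not remove the conflict: SAP 2.1.1 names safety parameters expressly and says their baselines are shown with the on-treatment summaries, so someone working from the SAP would have reason to apply it.

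It can also be said that this is loose drafting and that pre-dose Visit 3 values were meant to count. That is plausible, since no change is declared in SAP 1.5 or 1.6. But the text does not say so, and the same edit would be needed.

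Other points that stand:

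- The size depends on an assumed SD and on how the highest-value rule is read.
- The longer rest at Visit 1 (10 against 5 minutes) may lower those readings and offset part of the fall, by an amount the documents do not give.
- An unscheduled measurement between Visits 1 and 3 could serve as baseline for individual patients.

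A reader might infer that the trial has settled on Visit 1 as baseline, that blood pressure safety is compared unfairly between the arms, or that a real rise would go unseen. The documents support none of these. The protocol rule points to Visit 3. The artifact is common to both arms. Protocol 11.4.3 also reports absolute values at each visit, and the incidence of potentially clinically significant abnormalities regardless of baseline level.

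**Conclusion.** The inconsistency is real: SAP 2.1.1 conflicts with Protocol 11.4.3 for safety parameters and with SAP 2.1.3 for efficacy parameters, and it is undeclared. Applied literally, it makes Visit 1 the scheduled baseline for blood pressure, pulse and weight, and the descriptive within-arm change in blood pressure would tend to show an artificial fall.

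On an assumed systolic SD of 3 to 8 mmHg the fall is about 1.5 to 8 mmHg systolic, before any offset from the longer rest at Visit 1. Only the direction of the selection effect rests on the documents' own procedure; the mmHg figures are illustrations.

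The comparison between arms, the absolute values by visit and the abnormality summaries defined regardless of baseline are not biased by this. The scheduled HbA1c, FPG and CGM baselines, and so the primary endpoint, are unaffected. Pulse and weight are affected only in that their baseline moves earlier, into screening. This is a minor correction, worth making because the remedy is so small.

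**What to change.** In SAP 2.1.1, replace the reference to Visit 3 with the wording of SAP 2.1.3, so that baseline "is defined as the last available value before the first injection of IMP". Add that vital signs and weight measured at Visit 3 before the first injection are the baseline. The pre-dose condition is needed because Protocol 10.1.2 does not say whether these measurements come before the supervised injection.

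If the Visit 3 blood pressure is missing and a Visit 1 value is used in its place, flag it, because it was recorded under a different rule.

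The cost is one or two SAP sentences and a flag. The Visit 3 data are already scheduled for collection.

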2.1.2 Prior or concomitant medications

All medications will be coded using the World Health Organization-Drug Dictionary (WHO-DD) using the version currently in effect at Sanofi at the time of database lock.

- Prior medications are those the patient used within 3 months before screening and from screening to first investigational medicinal product (IMP) intake. Prior medications can be discontinued before first administration or can be ongoing during treatment phase.
- Concomitant medications are any treatments received by the patient concomitantly to the IMP, from first injection of IMP to the last injection of IMP + 1 days. A given medication can be classified both as a prior medication and as a concomitant medication.
- Post-treatment medications are those the patient took in the period running from the last injection of IMP + 2 days (or 1 day for anti-diabetic therapies) to the end of the study.

The IMP includes basal insulin of Toujeo and Lantus as the testing and control medications, respectively. Mealtime insulin analogs (glulisine, lispro or aspart) are the study required concomitant antidiabetic medication, which is defined as the NIMP in this study.

During the study following medications are prohibited.

- Any antidiabetic agents other than the study medications mentioned above, including oral or injectable antihyperglycemic agents, other type of basal insulin (eg, NPH, Detemir, premixed insulin), and human regular insulin,
- Insulin pump therapy is not allowed during the course of the study,

- Initiation of any weight loss drugs is not allowed; previous treatment with weight loss drugs can be continued and doses must remain stable throughout the study,
- Systemic glucocorticoids for more than 10 consecutive days (topical or inhaled applications are allowed),
- Medications containing acetaminophen/paracetamol during the period of CGM performance as these medications can interact with the glucose sensor of the CGM device.

Other medications which are unlikely to interfere with the IMP and the study variables are allowed as needed and discussed with the investigator. However, doses of chronically administered medicines should be kept fixed during the trial if at all possible.

Any technical details related to computation, dates, imputation for missing dates are described in [Section 2.5](#).

2.1.3 Efficacy endpoints

The baseline value for efficacy parameters is defined as the last available value before the first injection of IMP.

Baseline CGM measurements will start at Visit 2 and stop at randomization visit (Visit 3).

Observation period for efficacy endpoints

- The on-treatment period for efficacy variables is defined as the time from the first dose of IMP up to:
 - Seven (7) days after the last dose of IMP for HbA1c,
 - One (1) day after the last dose of IMP for hypoglycemia,
 - One (1) day after the last dose of IMP for FPG, SMPG and CGM,
 - Zero (0) day after the last dose of IMP for insulin glargine dose.
- The randomized period for efficacy variables is defined from the first dose of IMP up to Week 16 (visit 19).

All efficacy parameters will be performed on on-treatment period and randomized period.

All CGM derived variables will be subject to the following criteria.

1. CGM data are blinded to both the patients and investigators.
2. During the CGM performing week, the IMP insulin (Toujeo or Lantus) dose is fixed without a change, while the mealtime insulin dose can still be adjusted appropriately.

3. A complete 24-hour CGM profile includes 288 data points given that CGM reading is recorded every 5 minutes.
4. The start and end time of a 24-hour CGM profile is defined as midnight. i.e. each CGM profile begins at midnight (hour 0) and ends at midnight (hour 24 = hour 0). Partial CGM data points prior to the first midnight and after the last midnight from the visit will not be used in the CGM parameter calculation as the partial CGM profile may introduce additional variabilities to the data.
5. Useable CGM data for a day/a 24-hour CGM profile are defined as at least 85% time of records (245 data points) without a gap (missing data) lasting for ≥ 2 hours per 24 hours. At least 4 days of qualified 24-hour CGM records for each patient will be used for efficacy analyses. If the partial CGM data described in previously have at least 85% of a full CGM profile or 245 data points, the partial CGM profile will be used to calculate CGM parameters.
6. In cases that there are more than 288 data points or more than one data point per 5 minutes, usually due to recalibration or switching CGM devices, it will be reviewed and treated case by case. Usually averaging the data points every 5 minutes will be performed so that there is only one data point per 5 minutes.
7. Per protocol, during Week 15, patients will wear a blinded CGM device for 7 consecutive days to generate minimum 4 days of useable CGM data. If a patient fails the first attempt for any reason, he/she will be retrained for CGM conduct and complete another course of blinded CGM in Week 16. If the patients fails the first week of CGM, only the second week CGM data will be used for data analysis and determine whether there are sufficient data to derive CGM variables per steps 1-6 above. If the second week of CGM data are not sufficient per steps 1-6 above either, CGM data from the first week and the second week will be pooled together to repeat steps 1-6.
8. If a patient prematurely withdraws from the study before Week 15 (visit 18) the CGM data will be missing for the individual patient and the patient will be excluded from the primary efficacy analyses.
9. For all CGM parameters except the total and between day coefficient of variations (CV%) and standard deviations and area under the curve of glucose concentrations, a CGM parameter will be first calculated based on each 24-hour CGM profile from the visit, the final values of the CGM parameters for the visit will be based on the average of parameter values taken on each CGM profile from each CGM visit.

